7.1 DEMOGRAPHIC AND OTHER BASELINE CHARACTERISTICS

Only descriptive statistics are planned for this section of the CTR.

[figure not shown]
Descriptive statistics will be presented by treatment for demographic parameters and baseline characteristics, based on the RS. The presence of mutations (yes or no) in the following genotypes will be descriptively presented by treatment for the RS: IL36RN, CARD14, or, AP1S3 based on information collected via eCRF and the results for the DNA resequencing respectively.

Characteristics of the trial disease, including details on the current and past GPP flares prior to trial onset, will be displayed for randomized patients. Here the output for most recent flare will be based on “Disease Characteristics (Most Recent Flare prior to Consent)” eCRF page while other prior flares will be based on “Natural Medical History for GPP” eCRF page.

For the continuous variables described below, the following categories will be defined, and presented according to the number and percentage of patients in each category:

Table 7.1: 1 Categories for summary of continuous variables

Variable	Categories
Age	< 50 years 50 to < 65 years ≥ 65 years < 65 years ≥ 65 years
Weight	≤ 70 kg > 70 to ≤ 80 kg > 80 to ≤ 90 kg > 90 kg
BMI	< 25 kg/m ² 25 to < 30 kg/m ² ≥ 30 kg/m ²
Time since first diagnosis	≤ 1 year > 1 to ≤ 5 years > 5 to ≤ 10 years > 10 years

7.2 CONCOMITANT DISEASE AND MEDICATION

Only descriptive statistics are planned for this section of the report. Analyses of concomitant diseases and medication will be based on the RS.

Concomitant diseases (i.e. baseline conditions) and concomitant non-drug therapies will be coded according to the most recent version of MedDRA. Concomitant medications will be coded according to the most recent version of the World Health Organisation – Drug Dictionary.

A medication/non-drug therapy will be considered concomitant to treatment, if it

- is ongoing at the start of randomized trial treatment or
- starts within the on-treatment period (see [Section 6.1](#) for a definition of study analysis phases).

A medication/non-drug therapy will be considered as prior medication/non-drug therapy, if the end date of the medication/therapy is at any time prior to the start of randomized trial treatment.

Concomitant medication use (excluding escape medications as defined in the CTP) will be summarized with frequency and percentage of patients by ATC3 class and preferred name.

The frequency and percentage of patients with historical medication for GPP will be displayed, including presentation by type of historical medication (preferred name), and by reason for discontinuation.

The frequency and percentage of patients taking either none or any background medication for GPP will be tabulated by type of background therapy (preferred name); a background therapy is assumed to be present if the medication is identified on the CONMED page of the CRF and is given for the purpose of disease under study (flagged as a background medication).

Use of escape medication, treatment with OL Spesolimab at Day 8, or rescue treatment with Spesolimab will be summarised separately (see [Section 7.6.3](#)). An escape medication is assumed if for any medication which is newly given for the disease under study and denoted for the purpose of escape use (disease worsening/not improved) per CONMED page of the CRF.

Concomitant use of non-drug therapies will be summarised with frequency and percentage. Summaries will be presented in the same manner as done for the concomitant medication use.

7.3 TREATMENT COMPLIANCE

Only descriptive statistics are planned for this section of the report.

Treatment compliance to the randomized study treatment will be summarised on Day 1 via dose intensity (as described in [Section 5.4.6](#)) for the SAF using descriptive statistics (N, mean, SD, minimum, median, maximum).

The number and percentage of patients with the following overall compliance categories will be presented:

- "< 80% of planned",
- ">=80 of planned"

7.4 PRIMARY ENDPOINT

The evaluation of patients achieving a GPPGA pustulation subscore of 0 at Week 1 is the primary endpoint of this trial.

Death, or any use of escape medication prior to observing the primary endpoint(s) is considered to reflect a failure to achieve the endpoint outcome, i.e. non-response. In this concept, death, or any use of escape medication after the actual assessment time point of week 1 is not considered. If time is not collected, death or any use of escape medication on or after the actual assessment day of Week 1 is not considered.

The Suissa-Shuster Z-pooled test, will be implemented to test the treatment effect on the primary endpoint on the RS (estimand EN), at a 1-sided, alpha level of 0.025. Confirmation of efficacy is then given only if the null hypothesis on the primary endpoint is rejected. In the output, the result will be reported at 2-sided alpha level of 0.05 which is more common way in CTR but it is exactly same as 1-sided alpha level of 0.025. Confidence intervals (95%) around the risk difference will be produced using the Chan and Zhang method ([6](#)).

Example SAS code for Suissa-Shuster Z-pooled test is as follows:

```
PROC FREQ DATA=data;
  TABLES treat*endpoint_bin;
  EXACT BARNARD (column=2);
RUN;
```

Example SAS code for CI of proportion difference by Chan and Zhang method is as follows:

```
PROC FREQ DATA=data;
  <WHERE treat IN ('Treatment_1','Treatment_2');>
  TABLES treat*endpoint_bin / RELRISK RISKDIFF;
  EXACT RELRISK (METHOD=SCORE column=2) RISKDIFF (METHOD=SCORE
  column=2);
RUN;
```

Graphical displays (Line plots) of the response on primary endpoint will be produced over time (with 95% confidence intervals based on the Wilson score) up to, and including, Visit 14 (Week 12).

Secondary analysis for the primary endpoint will include:

- A sensitivity analysis utilizing the PPS;
- Sensitivity analyses on the RS which utilize alternative methods for the handling of missing data as described in [Section 6.6.2](#).
- Analysis of an additional estimand (EN-PC) whereby death or any use of escape medication, prior to observing the week 1 primary endpoint will be considered to

represent a non-response. For patients who use restricted medication for other purpose prior to Week 1, data will be censored for further analysis following the restricted medication use and imputed using NRI method as described in [Section 6.6.2](#).

- Sensitivity analyses on the RS to adjust for the potential covariates, IL36R mutation status (Yes vs No) and baseline GPPGA total score (3 vs 4) respectively.

The proportion of patients with a response between Spesolimab and placebo will be analysed by IL36R mutation status and baseline GPPGA total score (3 vs 4) respectively, using a logistic regression approach with a logit link via PROC LOGISTIC in SAS®. Fixed classification effects will include treatment, subgroup and treatment-by-subgroup interaction term.

The estimates from the logistic regression are on the logit scale, and the difference in proportions will be calculated as the difference between the predicted probabilities by subgroup level and treatment on the original scale.

Descriptive subgroup displays on the primary endpoint (via estimand EN) will be done for the applicable subgroups as defined in [Section 6.4](#) using the RS.

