3.3.4 Initiation of randomized treatment

Treatment (Visit 2) will be initiated immediately in patients:

- Who meet the inclusion criteria ([Section 3.3.2](#)).
- Who are presenting with an acute GPP flare with moderate to severe intensity, defined by emergence of:
 - a) GPPGA score of at least 3 (moderate), and
 - b) presence of fresh pustules (new appearance or worsening of pustules), and
 - c) GPPGA pustulation sub score of at least 2 (mild), and
 - d) at least 5% of Body Surface Area (BSA) covered with erythema and the presence of pustules
- And who do not meet any of the exclusion criteria ([Section 3.3.3](#)).

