7. STATISTICAL METHODS AND DETERMINATION OF SAMPLE SIZE

7.1 STATISTICAL DESIGN – MODEL

This trial is designed as a randomized, parallel-group, double-blind, and placebo-controlled trial with one active dose of BI 655130 in patients with GPP presenting with an acute flare of moderate to severe intensity.

The primary objective of this trial is to evaluate the efficacy, safety and tolerability of a single i.v. dose of BI 655130 in comparison to placebo at Day 1. The primary analysis, on each of the binary, primary endpoint, achievement of a GPPGA pustulation subscore of 0 at Week 1, and key secondary endpoint, achievement of a GPPGA of (0, 1) at Week 1, where any use of escape medication prior to observing the endpoint is considered to be a non-response, will compare the proportion of patients who achieve a response on BI 655130 to Placebo. Given the small sample size proposed to be used in this trial, an exact statistical test, the Suissa-Shuster Z-pooled test, will be used to perform the primary analysis. Confirmation of efficacy is then given if the proportion of patients achieving a response on the primary endpoint is statistically significantly higher for BI 655130 than for placebo. Formal statistical hypothesis testing will be performed at an overall 1-sided alpha level of 0.025.

Stratification of randomization will be performed in this trial for Japan versus non-Japan. This stratification is implemented for operational purposes only and is not intended to be used as an adjustment factor in the primary analyses of efficacy (see [Section 7.6](#)).

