7.3.1 Primary endpoint analyses

The analysis for the primary endpoint includes the evaluation of patients achieving a GPPGA pustulation subscore of 0 at Week 1.

Any use of escape medication, e.g. use of restricted medication for disease worsening in [Table 4.2.2.1: 1](#), prior to observing the primary endpoint is considered to reflect a failure to achieve the endpoint outcome, i.e. non-response (see primary endpoint definition in [Section 2.1.2](#)).

Due to the small sample size of the trial, an exact statistical test will be used to assess the statistical significance of the treatment effect versus Placebo. Since the traditional Fisher's exact test may be unnecessarily conservative, an alternative test, the Suissa-Shuster Z-pooled test, will be implemented in this trial. The Suissa-Shuster Z-pooled test always preserves the type I error level and is usually more powerful than the Fisher's exact test.

The primary endpoint will be tested, for the RS, using the Suissa-Shuster Z-pooled test at a 1-sided, alpha level of 0.025.

Secondary analysis of the primary endpoint will include:

- A sensitivity analysis utilizing the PPS;
- Analysis of an additional estimand whereby any use of escape medication prior to week 1 will be considered to represent a non-response. For patients who use other restricted medication but not for disease worsening prior to Week 1, data will be censored for further analysis following the use and imputed using the methods described in [Section 7.5](#).
- Sensitivity analyses which utilize alternative methods for the handling of missing data as described in Section 7.5.
- A subgroup assessment according to the Japan vs. non-Japan strata will be assessed descriptively
- Sensitivity analyses to adjust for the covariates, IL36R mutation status (Yes vs. No) and baseline GPPGA total score (3 vs. 4) respectively using logistic regression.

Further analysis of the primary endpoint will include:

- Analysis of the time to first achievement of a response on the primary endpoint via Kaplan-Meier methods.

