7.5 SECONDARY ENDPOINT

7.5.1 Key Secondary endpoint

The treatment effect on the key secondary endpoints will be tested in a hierarchical manner subsequent to the test of the primary endpoint. The key secondary endpoint on the patients achieving a GPPGA score 0 or 1 at Week 1 will be analyzed in the same way as primary endpoint.

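### SAP 7.4's covariate-adjusted sensitivity analysis is a saturated subgroup model with no adjusted overall risk difference specified (minor)

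*SAP*

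**What the plan says.** Protocol 7.3.1 lists, among the secondary analyses of the primary endpoint, "Sensitivity analyses to adjust for the covariates, IL36R mutation status (Yes vs. No) and baseline GPPGA total score" (3 v 4), each in turn, by logistic regression. It mentions no interaction. The SAP 7.4 bullet keeps the same purpose: "Sensitivity analyses on the RS to adjust for the potential covariates, IL36R mutation status" and baseline GPPGA, again one at a time.

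The SAP text under that bullet then describes response analysed by each covariate, with this model: "Fixed classification effects will include treatment, subgroup and treatment-by-subgroup interaction term". Estimates come on the logit scale, and for the risk scale "the difference in proportions will be calculated as the difference between the predicted probabilities by subgroup level and treatment on the original scale". No averaging over covariate levels and no interval method is given for this analysis.

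The result it would be compared with is a single overall figure: "Confidence intervals (95%) around the risk difference will be produced using the Chan and Zhang method". SAP 7.5.1 says the key secondary endpoint "will be analyzed in the same way as primary endpoint", so the same analysis applies there. Neither covariate is a randomisation factor: "Stratification of randomization will be performed in this trial for Japan versus non-Japan" (Protocol 7.1).

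**The concern.** An analysis that adjusts for a covariate should give a treatment effect that can be set beside the unadjusted one, to show whether chance imbalance on that covariate moved the result. With 34 v 17 patients and no stratification on either covariate, such imbalance is to be expected. The model specified gives separate effects at each covariate level. If a reader later asks for the adjusted figure, it can be computed from the four cells, but the weights and the interval method would then be chosen after unblinding.

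**Working it through.** **Inputs.** Allocation 34:17 and expected response 60% v 10% come from Protocol 7.7. The plan gives no figure for this analysis. Its power figures reproduce from these inputs: an exact Suissa-Shuster calculation gives 96.28% for the primary endpoint (stated 96.3%), and simulation with correlation 0.65 gives 93.9% for both endpoints (stated 93.9%). The documents give no share of patients with baseline GPPGA 4 and no covariate effect on response. Subgroup shares of 21% and 50% are therefore assumptions; 21% is the proportion with recessive IL36RN alleles in the meta-analysis cited in Protocol 1.1. Covariate odds ratios are also assumed.

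**Saturation.** Mutation status is yes/no. Baseline GPPGA is 3 or 4, because Protocol 3.3.4 requires at least 3. For treatment T and covariate S the model is logit p = b0 + b1·T + b2·S + b3·T·S. Four parameters fit four cells, so each fitted probability equals its observed proportion.

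**Illustration (assumed counts).** Responders 20/34 v 2/17. Covariate-positive 10/34 v 3/17, with responders 8/10 and 1/3; covariate-negative responders 12/24 and 1/14.
- Unadjusted: 20/34 − 2/17 = 0.471.
- SAP model: 0.467 (positive) and 0.429 (negative). These equal 8/10 − 1/3 and 12/24 − 1/14.
- Mantel-Haenszel, with weights n1·n0/N: 10·3/13 = 2.308 and 24·14/38 = 8.842. The estimate is (2.308·0.4667 + 8.842·0.4286)/11.150 = 0.436, which is 3.4 points below the unadjusted figure.

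The imbalance here is 29.4% − 17.6% = 11.8 points. That is ordinary: the SD of the difference in share is sqrt(s(1−s)(1/34 + 1/17)), or 12.1 points at s = 21% and 14.9 at s = 50%.

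**Gap between unadjusted and Mantel-Haenszel differences.** 200,000 simulated trials per scenario, 60% v 10%, shares 21% / 50%:

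| Covariate odds ratio | 95th percentile (points) | Gap above 5 points (% of trials) |
|---|---|---|
| 1 | 4.1 / 4.1 | 2.9 / 3.0 |
| 2 | 5.2 / 5.9 | 5.7 / 7.6 |
| 3 | 6.5 / 7.6 | 9.7 / 13.9 |
| 4 | 7.2 / 8.8 | 13.1 / 19.3 |

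The odds-ratio-1 row is noise, so a gap of up to about 4 points tells the reader little.

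**Interval method.** 60,000 trials in each of 32 scenarios (share 21 to 50%, placebo 5 to 20%, odds ratio 1 and 3). Coverage of nominal 95% intervals:
- SAP model averaged over the covariate, plug-in variance: 91.1 to 92.4%. Not estimable in about 2% of trials at a 21% share.
- Mantel-Haenszel, Sato variance: 92.5 to 93.2%.
- Mantel-Haenszel, score-type (Sato variance evaluated at the hypothesised difference): 94.3 to 96.0%.

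Mantel-Haenszel was unbiased to within about 0.2 points.

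**By-level precision.** The overall 95% half-width is 1.96·sqrt(0.6·0.4/34 + 0.1·0.9/17) = 21.8 points. Dividing by sqrt(0.5) gives 30.8 points per level at an even split. Dividing by sqrt(0.21) and sqrt(0.79) gives 47.5 and 24.5 points. Neither level can stand in for an overall adjusted figure.

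**The case against.** The strongest reply is that the analysis does what it was added for. The rationale in Protocol 11.2 (Global Amendment 2) is to see whether the two covariates are related to the endpoint. A model with covariate and interaction terms addresses that, and its logit-scale estimates are available as well as the by-level differences. The protocol names logistic regression but promises no overall risk difference. On this view the only fault is the word adjust on a subgroup analysis.

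Much of this stands, and it is why the point is minor. What remains is that the current text of both documents gives adjustment as the purpose, and nothing visible delivers an adjusted effect.

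Two stronger readings might be inferred, and the documents support neither. One is that the efficacy conclusion is at risk from covariate imbalance. The confirmatory test is the unadjusted Suissa-Shuster test, which this analysis does not enter. The other is that sparse cells make the analysis unusable. At a 10% placebo rate and assumed placebo splits from 8/9 to 3/14, at least one placebo cell has no responders with probability 65% to 79%, and the logit coefficients then diverge. The by-level risk differences can still be computed.

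SAP 6.4 and section 9 are not in the supplied text and could add detail. SAP 7.4, however, states the model and its output without a visible gap, and cites 6.4 only for the separate descriptive subgroup displays.

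**Conclusion.** The point holds as a minor one. Followed as written, the labelled adjustment yields raw by-level risk differences, and no covariate-adjusted overall risk difference is specified in the supplied text for either Week 1 endpoint. The exact test, the one-sided 0.025 alpha, the power and the confirmatory conclusion are unaffected.

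The missing figure would usually be close to the unadjusted one. Even 7.6 points is about a third of the 21.8-point overall half-width, and it needs an assumed odds ratio of 3. The saturation argument is algebra and rests on no assumption beyond one binary covariate per model. The gap sizes depend on the assumed shares and odds ratios.

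**What to change.** - Keep the by-level results and label them a subgroup analysis.
- For each covariate and both Week 1 endpoints, pre-specify one Mantel-Haenszel risk difference stratified by that covariate, with a score-type 95% CI, shown beside the primary risk difference. Record it in SAP section 4 as a change from the protocol's logistic regression.
- State which source of mutation status is used and how unknown status is handled. SAP 7.1 names both the eCRF and DNA resequencing. Protocol 6.2.1 collects historical status only where available, while 6.2.2 plans genotyping for all patients. The SAP history table mentions a fallback from central laboratory to eCRF results, but its subject is blacked out. If it concerns mutation status, a cross-reference settles the source.

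A Firth-penalised main-effects logistic model, standardised over the randomised set, would stay closer to the protocol, but I would not use it. In 60,000 trials per scenario with an irrelevant covariate, its risk difference fell below the unadjusted one in 97% of trials, by 3.0 points on average. The mean gap was the same when the arms were balanced within 3 points on the covariate. That shrinkage is comparable to the gaps the check is meant to reveal.

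The cost is one SAP paragraph, a section 4 entry and four estimates (two covariates, two endpoints), with no new data.

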7.5 SECONDARY ENDPOINT

7.5.1 Key Secondary endpoint

The treatment effect on the key secondary endpoints will be tested in a hierarchical manner subsequent to the test of the primary endpoint. The key secondary endpoint on the patients achieving a GPPGA score 0 or 1 at Week 1 will be analyzed in the same way as primary endpoint.

7.5.2 Secondary endpoints

Secondary endpoints included in the testing procedure

The treatment effect on the following secondary endpoint will be tested in a hierarchical manner as a part of the pre-specified testing strategy (see Section 7.2 of the CTP), subsequent to the test of the primary endpoint and key secondary endpoint:

- 1) The proportion of patients achieving a GPPASI 75 at Week 4,
- 2) The change from baseline in pain VAS score at week 4,
- 3) The change from baseline in PSS score at week 4, and,
- 4) The change from baseline in the total FACIT-Fatigue score at Week 4.

GPPASI 75 at Week 4

The primary analysis for the proportion of patients achieving a GPPASI 75 at Week 4 will be performed using the same approach as that defined for the primary analysis of the primary endpoint, based on the RS (estimand EN).

Graphical displays will be produced using the same method as described for the primary endpoint.

Sensitivity analysis for GPPASI 75 at Week 4 will include:

- Sensitivity analyses on the RS which utilize BRI respectively for the handling of missing data as described in [Section 6.6.2](#).

Descriptive subgroup displays (via estimand EN) will be done for the applicable subgroups as defined in [Section 6.4](#) using the RS.

Pain VAS score, PSS score, and FACIT-Fatigue score at Week 4

For the analysis of each of the continuous secondary endpoints which are included in the statistical testing strategy, the following approach will be done:

Any assessments after death, or the use of escape medication, or OL Spesolimab at D8, or rescue medication with Spesolimab, will be considered as “non-response” and assigned with worst outcome for the analysis (estimand EN). In this concept, death, or any use of escape medication or OL Spesolimab at Day 8 or of rescue medication with Spesolimab after the actual endpoint assessment time point at week 4 is not considered. If time is not collected, death, or any use of escape medication or of rescue medication with Spesolimab on or after the actual assessment day of Week 4 is not considered.

In primary analysis of the secondary continuous endpoints, “non-response” itself is not a missing value but the worst possible outcome of the endpoint. The mean of the endpoints could not be reported due to the mix of “non-response” outcomes and other numeric continuous outcomes. The Q1, median and Q3 could be still reported, however, where “non-response” will be treated as the worst outcome in the rank. If the proportion of “non-response” is high enough, Q1, median and Q3 of the endpoint could all be reported as “non-response”. For example, for a continuous endpoint where larger value indicates the better outcome, if the achieved data is (NR, NR, NR, NR, NR, NR, 2, 3, 3, 3, 5) where NR=“non-response”, then Q1 is NR, median is NR and Q3 is 3.

For each secondary continuous endpoint, the effect of Spesolimab will be evaluated by a Wilcoxon rank test using the RS. All details regarding the ranking rules for Wilcoxon test are defined in [Section 6.6.2](#).

Example SAS code for Wilcoxon rank test is as below:

```
proc NPAR1WAY data=data wilcoxon;
```

```
  class treatment;  
  var endpoint;  
  exact wilcoxon;
```

run;

The difference between treatments, based on the RS, will be displayed using a modified Hodges-Lehmann (HL) estimate of the median difference (11). If a patient has died or used escape medication, or OL Spesolimab at D8, or rescue medication with Spesolimab prior to a timepoint (i.e., Week 4), then the patient's assessment at that timepoint (i.e., Week 4) will be treated as "non-response" in HL estimation. Otherwise, missing data at that timepoint (i.e., Week 4) will be imputed using LOCF method. The modification of the HL estimate is that all NR-NR comparisons on a patient level will be excluded from the calculation since they do not provide any information about the numerical estimate and they have no clear 'positioning' when calculating the median. Further the difference between a non-missing value and a non-response status should be 'large positive' or 'large negative', depending on the direction. A 95% confidence interval around the modified HL estimate of the median treatment difference will also then be calculated, adjusting for the reduced number of comparisons (due to exclusion of the NR-NR outcomes). Graphical displays of the modified HL estimate of the median treatment difference (with and without 95% confidence intervals) will be produced over time. For clarity, a full description of the modified HL method is defined as follows:

For each of the secondary continuous endpoints in the testing procedure, assume that the continuous response vector in Placebo arm is (x_1, x_2, \dots, x_n) and the continuous response vector in Spesolimab arm is (y_1, y_2, \dots, y_m) , where n is the number of patients in Placebo arm and m is the number of patients in Spesolimab arm.

Step 1, In line with the standard HL approach, calculate the difference between every possible pair of x 's and y 's; $d_{ij}=y_j-x_i$. There will be a total of m times n such differences. For the modified version, all NR-NR comparisons are then discarded from the calculation, that is, $mn-1$ comparisons will be performed (where 1 is the number of NR-NR comparisons). Note that all comparisons between a non-response and a measurement are still retained. The remaining values in the list of d_{ij} will then be ranked in ascending order and the median from the list will be picked as the modified HL estimate.

Step 2, Compute the rank of the lower confidence limit as

$R_L = \frac{mn'}{2} - Z_{0.025} \sqrt{\frac{m'n'(m'+n'+1)}{12}}$ where $Z_{0.025}$ is the z-value corresponding to a one sided 97.5% confidence interval, $m' = \sqrt{m^2 - mn/n}$ and $n' = m'n/m$ and noting that $m'n' = mn-1$. If R_L is a non-integer, it needs to be rounded down. The rank of the upper confidence limit will be $R_U = m'n' - R_L + 1$. If the obtained R_L or R_U is not a possible value, then it should be rounded to the nearest possible value.

Step 3, Look up the values that corresponding to the ranks R_L and R_U in the remaining values in the ranked list of d_{ij} . These are the confidence limits for HL estimate.

Note that if the overall non-response rate across two arms is too high (i.e., >30%), the modified HL estimate will be no longer robust and therefore will not be displayed.

Descriptive statistics, based on RS (OC) and RS (OC-IR), will be produced, and will include n, mean, SD, min, median, and max for the individual treatment groups.

Sensitivity analysis for each of the continuous secondary endpoints will include an additional estimand (EC) whereby any data post use of escape medication/OL Spesolimab at D8/rescue treatment with Spesolimab will be censored. Two methods will be used to handle the censored or other missing values respectively:

- MMRM method (EC-MMRM),

Continuous endpoints up to week 4 will be evaluated using an MMRM model accounting for the following sources of variation: ‘baseline’, ‘visit’ and ‘treatment’ as covariates, ‘visit*treatment’ and ‘visit*baseline’ as interaction effects as well as the random ‘subject’ effect. The unstructured covariance structure will be used to model the within patient measurements. To estimate denominator degrees of freedom the Kenward-Roger approximation will be used.

It is expected most of patients on placebo arm may receive escape medication up to Day 8 or OL Spesolimab at Day 8. Based on “EC” estimand, then most placebo data post Day 8 may have been censored. To avoid achieving the estimates which are not robust, if from certain visits, the values of more than 70% patients are censored or missing for one treatment arm, then MMRM estimates won’t consider the data from that time point for that arm.

In the event of any model non-convergence, the methods described in [Section 9.2](#) will be utilized to resolve this.

Example SAS code for MMRM is as below:

```
PROC MIXED DATA=alldat cl method=reml;
  CLASS visit trt subject;
  MODEL ept = visit*trt base*visit / ddfm=kr s CL;
  REPEATED visit / subject= subject type=un r rcorr;
  LSMEANS visit*trt / pdiff=all om cl alpha=0.05 slice=visit;
RUN;
```

Results of the MMRM (N, mean, SE and 95% CI per dose group and timepoint) will be presented in tables and displayed graphically.

- LOCF method (EC-LOCF).

In addition, subgroup displays will be done for the applicable subgroups as defined in [Section 6.4](#) using the RS in the following two ways:

- Descriptive statistics using primary EN estimand and impute missing values using LOCF method.
- MMRM method using EC estimand,

Subgroup analysis will use MMRM model based on the alternative estimand (EC). A single MMRM model will be fitted involving all terms from the above EC-MMRM model in the sensitivity analysis except replacing the treatment-by-visit term by the treatment-by-subgroup-by-visit term.

[figure not shown]
To avoid achieving the estimates which are not robust, if from certain visits, the values of more than 70% patients are censored or missing across all subgroup levels for one treatment arm, then MMRM estimates won't consider the data from that time point for all subgroups of that arm.

In the event of any model non-convergence, the methods described in [Section 9.2](#) will be utilized to resolve this.

Secondary endpoints not included in the testing procedure

[figure not shown]
For the binary secondary endpoints (either at week 1 or at week 4) that, are not included into the statistical testing strategy, graphical displays and statistical testing using the Suissa-Shuster Z-pooled test will be performed using the primary estimand and imputation strategy (EN-NRI), as described for the primary endpoint in [Section 7.4](#).

[figure not shown]
For the continuous secondary endpoints, the percentage change in GPPASI from baseline at Week 1 and Week 4, which are not included into the statistical testing strategy, the analysis will be performed using the same method as for the secondary continuous endpoints in the testing strategy. All details regarding the ranking rules for Wilcoxon rank tests are defined in [Section 6.6.2](#) (and [Table 6.6.2: 2](#)).

[figure not shown]

[figure not shown]

[figure not shown]

[figure not shown]

